### **3 STUDY OBJECTIVES**

#### **3.1 Primary Objective**

- To evaluate the effect of tenapanor on change in s-P levels when tenapanor is administered orally twice daily for 28 days as adjunctive therapy to ESRD subjects with hyperphosphatemia on stable phosphate binder therapy.

#### **3.2 Secondary Objective**

- To evaluate the effect of tenapanor versus placebo as adjunctive therapy with phosphate binder to lower subject's s-P level to <5.5 mg/dL.
- To evaluate the effect of tenapanor versus placebo as adjunctive therapy with phosphate binder on intact fibroblast growth factor 23 (iFGF23) and c-terminal fibroblast growth factor 23 (cFGF23).
- To evaluate the effect of tenapanor versus placebo as adjunctive therapy with phosphate binder on parathyroid hormone (PTH).

### 3.3 Exploratory Objective

- To collect and store plasma/serum for future exploratory research into serum/plasma biomarkers related to cardiorenal disease and/or bone metabolism or that may influence the response (i.e. distribution, safety, tolerability, and efficacy) to tenapanor. These data will not be part of the clinical study report.

[figure not shown]
## 4 STUDY DESIGN

### 4.1 Design Summary

This is a randomized, double-blind, placebo-controlled study to evaluate the efficacy of tenapanor as adjunctive therapy to phosphate binder therapy in ESRD subjects with hyperphosphatemia.

The study consists of a Screening visit; a Run-in Period of at least 2 weeks and up to 4 weeks, where existing phosphate binder treatment is maintained; and a 4-week Double-Blind Treatment Period, during which subjects are randomized in a 1:1 ratio to receive tenapanor or placebo at a dose of 30 mg twice daily (bid; three 10 mg tablets each time) while continuing their existing phosphate binder treatment. The dose of phosphate binder should remain unchanged throughout the study (from Screening to the end of study). Approximately 214 subjects will be randomized at 40 to 50 sites.

**Figure 4-1: Study Design Diagram**

a Day 1 is the randomization day and serves as the reference day for all visits.

The Screening visit (Visit 1) and all other visits in the study must be scheduled after a short dialysis interval (Wednesday or Friday for subjects on a Monday-Wednesday-Friday schedule and Thursday or Saturday for subjects on a Tuesday-Thursday-Saturday schedule). Body weight, vital signs, and blood collections for laboratory assessments **must** be performed pre-dialysis. All other assessments may be performed pre-, during, or post-dialysis but should be performed at the same time at each visit.

At Screening, a subject must be on thrice daily phosphate binder therapy and have a s-P level  $\geq 5.5$  and  $\leq 10.0$  mg/dL to qualify for entering the study. The subject should be told to continue their existing phosphate binder treatment throughout the study without any change to the phosphate binder dose. Serum phosphorus will be measured at each visit (pre-dialysis after a short interval) during the Run-in Period to enable evaluation of the s-P randomization criteria. To be randomized at Day 1 (Visit 4), subjects must have a s-P level  $\geq 5.5$  and  $\leq 10.0$  mg/dL at Visit 3.

Subjects who do not meet the randomization criteria based on the s-P level at Visit 3 will be discontinued as screen failures. Subjects must continue to meet all other eligible inclusion/exclusion criteria at randomization. Subjects who meet the s-P criteria at Screening (Visit 1), but screen fail due to the s-P level at Visit 3 can be re-screened; they must wait a minimum of one week after screen failing to be re-screened.

During the Double-Blind Treatment Period, subjects will receive tenapanor or placebo starting at a dose of 30 mg bid (three 10 mg tablets each time). Tenapanor or placebo will be taken twice daily; just prior to breakfast and dinner. Subjects should **not** take study medication at the meal immediately preceding dialysis.

Investigators may decrease or increase the dose of study medication based on s-P levels and/or GI tolerability in 10 mg increments to a minimum of 10 mg bid or a maximum of 30 mg bid after Randomization (Visit 4) to Day 15 (Visit 6). Doses can be adjusted between visits.

Safety assessments will be performed at various time points throughout the study and will include physical examination, body weight, vital signs, safety laboratory tests, 12-lead electrocardiogram (ECG), and AE recording.

Blood samples will be collected, processed to serum or plasma, and stored, as appropriate, for the potential evaluation of exploratory biomarkers.

#### **4.1.1 Duration of Study**

The treatment duration of this study will be 4 weeks.

### **5 SELECTION AND WITHDRAWAL OF SUBJECTS**

#### **5.1 Inclusion Criteria**

A subject will be eligible for study participation if he/she meets the following criteria:

1. Signed and dated informed consent prior to any study specific procedures.
2. Males or females aged 18 to 80 years, inclusive, at Screening (Visit 1).
3. Females must be non-pregnant, non-lactating and fulfilling one of the following:
  - a. Post-menopausal defined as amenorrhea for at least 12 months following cessation of all exogenous hormonal treatments and with follicle stimulating hormone (FSH) levels in the laboratory defined post-menopausal range.
  - b. Documentation of irreversible surgical sterilization by hysterectomy, bilateral oophorectomy or bilateral salpingectomy, but not tubal ligation.
  - c. Use of acceptable contraceptive method: intrauterine device (IUD) with spermicide, a female condom with spermicide, contraceptive sponge with spermicide, an intravaginal system (e.g., NuvaRing®), a diaphragm with spermicide, a cervical cap with spermicide, or oral, implantable, transdermal, or injectable contraceptives, sexual abstinence, or a sterile sexual partner from Screening until 30 days after the last subject visit.
4. Males must agree to avoid fathering a child (or donating sperm), and therefore be either sterile (documented) or agree to use, from the time of enrollment until 30 days after end of study, one of the following approved methods of contraception: a male condom with spermicide, a sterile sexual partner, use of an IUD with spermicide by female sexual partner, a female condom with spermicide, contraceptive sponge with spermicide, an intravaginal system (e.g., NuvaRing®), a diaphragm with spermicide, a cervical cap with spermicide, or oral, implantable, transdermal, or injectable contraceptives.
5. Chronic maintenance hemodialysis (HD) 3x/week for at least 3 months or chronic maintenance peritoneal dialysis (PD) for a minimum of 6 months. If modality of dialysis has changed, subject must meet one of the two dialysis criteria above and been on the new modality of dialysis for a minimum of one month.
6. If receiving active vitamin D or calcimimetics, the dose should have been unchanged for the last 4 weeks prior to Screening (Visit 1).
7.  $Kt/V \geq 1.2$  at most recent measurement prior to Screening (Visit 1).

8. Prescribed and taking phosphate binder medication at least 3 times per day.  
The prescribed dose should have been unchanged during the last 4 weeks prior to Screening (Visit 1).
9. Serum phosphorus levels must be  $\geq 5.5$  and  $\leq 10.0$  mg/dL at Screening (Visit 1) and the end of the Run-in Period (Visit 3), analyzed at the central laboratory used in the study.
10. Able to understand and comply with the protocol.

## **5.2 Exclusion Criteria**

A subject will not be eligible for study participation if he/she meets any of the following exclusion criteria, or will be discontinued at the discretion of the Investigator if he/she develops any of the following medical conditions during the study:

1. Severe hyperphosphatemia defined as having an s-P level  $>10.0$  mg/dL on phosphate-binders at any time point during routine clinical monitoring for the 3 preceding months before Screening (Visit 1).
2. Serum/plasma parathyroid hormone  $>1200$  pg/mL. The most recent value from the subject's medical records should be used.
3. Clinical signs of hypovolemia at Screening (Visit 1) as judged by the Investigator.
4. History of inflammatory bowel disease (IBD) or irritable bowel syndrome with diarrhea (IBS-D).
5. Scheduled for living donor kidney transplant or plans to relocate to another center during the study period.
6. Use of an investigational agent within 30 days prior to Screening (Visit 1).
7. Involvement in the planning and/or conduct of the study (applies to both Ardelyx/CRO staff and/or staff at the study site).
8. If, in the opinion of the Investigator, the subject is unable or unwilling to fulfill the requirements of the protocol or has a condition which would render the results uninterpretable.

## **5.3 Subject Withdrawal**

Subjects are free to discontinue the study at any time, for any reason, and without prejudice to further treatment. The Investigator may remove a subject if, in the Investigator's judgment, continued participation would pose unacceptable risk to the subject or to the integrity of the study data. If possible, all procedures for early termination will be completed ([Section 8.7](#)).

#### **5.4 Early Termination of Study**

The study may be terminated at any time by the Sponsor if serious side effects occur, or if, in the Sponsor's judgment, there are no further benefits to be achieved from the study, or for administrative reasons. A site may be closed out if the Investigator does not adhere to the protocol or GCP. In the event that the clinical development of the investigational product is discontinued, the Sponsor shall inform all Investigators/institutions and the Institutional Review Board (IRB) overseeing the trial.

### **6 TREATMENT OF SUBJECTS**

#### **6.1 Administration of Investigational Product**

##### **6.1.1 Identity of Investigational Product(s)**

Tenapanor hydrochloride is an amorphous, off-white to white powder. Tenapanor tablets will be supplied as yellow, oval, biconvex tablets packaged in HDPE bottles with a desiccant canister. Each bottle contains sixty (60) 10 mg tablets and a desiccant canister. A matching placebo will be identically supplied in HDPE bottles.

##### **6.1.2 Treatments Administered**

All subjects will remain on their phosphate binder for the duration of the study. There should be no change to their phosphate binder dose for the duration of the study.

Tablets containing 10 mg of tenapanor or corresponding placebo will be taken orally twice daily just prior to breakfast and dinner. On dialysis days, subjects on HD should not take study medication at the meal immediately prior to dialysis and instead take it just prior to another meal. Each dose of one to three tablets will achieve total daily doses of 20, 40, or 60 mg tenapanor. If a meal is skipped, the dose should be taken with another meal during the day or at around the time that the meal would have been consumed.

##### **6.1.3 Dose Adjustments**

**All subjects will start at a dose of 30 mg bid** (three 10 mg tenapanor or placebo tablets each time). After randomization (Visit 4) to Day 15 (Visit 6), doses can be adjusted in 10 mg increments based on s-P levels and/or GI tolerability. Down-titration can go from 30 mg bid to 20 mg bid and 20 mg bid to 10 mg bid. Dose escalation can go from 10 mg bid to 20 mg bid, and 20 mg bid to 30 mg bid. Doses can be adjusted between visits.

#### **6.1.4 Method of Assigning Subjects to Treatment Groups**

After giving informed consent, subjects will be allocated sequential enrollment numbers at Screening (Visit 1).

A stratified randomization scheme will be employed to this study, with type of phosphate binder (sevelamer or non-sevelamer) and s-P level at Visit 3 ( $<7.5$  mg/dL or  $\geq 7.5$  mg/dL) as two stratification factors. The CRO or designated independent statistician will prepare the randomization scheme in accordance with the CRO's standard operating procedures (SOPs) and the randomization plan, which reflect Good Clinical Practice (GCP) standards. Upon completion of the Run-in Period, eligible subjects will be randomized in a 1:1 ratio at Visit 4 (Day 1) to receive tenapanor or placebo.

The randomization of this study will be implemented via an Interactive Response Technology (IRT). The IRT will allocate the treatment and provide the randomization number. The IRT will provide the appropriate bottle ID chosen from those bottle IDs available at the study site for tenapanor and placebo. As the randomization will not be stratified by study site, the assigned randomization numbers and the associated bottle IDs will not be sequential within a study site.

If a subject withdraws from the study, his/her enrollment and randomization numbers cannot be reused.

#### **6.2 Investigational Product Storage and Accountability**

##### **6.2.1 Storage Conditions**

The Investigator will ensure that all study medications are stored and dispensed in accordance with Food and Drug Administration (FDA) regulations concerning the storage and administration of investigational drugs.

Tablets of tenapanor and placebo should be stored in the original packaging according to the labeling.

##### **6.2.2 Drug Accountability**

The Investigator must ensure that all drug supplies are kept in a secure locked area with access limited to those authorized by the Investigator. The Investigator or the Investigator's designee must maintain accurate records of the receipt of all study medications shipped by the Sponsor or their representative, including but not limited to the date received, lot number, expiration date, amount received, and the disposition of all study medications. Current

dispensing records will also be maintained including the date and amount of study medications dispensed and the subject receiving study medications. All remaining study medications not required by regulations to be held by the clinical facility must be returned to the Sponsor or their representative immediately after the study completion.

### **6.3 Packaging and Labeling**

#### **6.3.1 Study Medication**

Tenapanor tablets (10 mg) are packaged in an opaque white HDPE bottle (60 tablets/bottle) with a white polypropylene child resistant closure and induction seal plus a desiccant canister.

A matching placebo will be identically supplied in HDPE bottles.

Study medications should be stored in the original packaging according to the labeling.

#### **6.3.2 Blinding Methods**

Placebo tablets are identical in appearance (shape, color, size, etc.).

Only the party responsible for labeling, warehousing and shipping drug supply; the CRO or designated independent statistician responsible for preparing the randomization list; and the IRT manager responsible for ensuring medication is available at sites will have knowledge of the treatments assigned during the Double-Blind Treatment Period.

### **6.4 Procedure for Breaking Randomization Code**

During the Double-Blind Treatment Period, the blind is to be broken only when the safety of the subject is at risk and knowledge of the study medication is essential to the clinical management of the subject. A decision to unblind a subject must be made in concert with the Medical Monitor and the Sponsor, except in emergency situations when the blind must be broken to determine the treatment for the subject. If a subject is unblinded, the date and reason for the unblinding must be recorded on source documents. Please refer to [Section 7.4](#) for reporting requirements.

### **6.5 Concomitant Therapy**

The use of concomitant medications during the Double-Blind Treatment Period, unless needed to treat an AE, should be the same as the medications used and recorded at Screening (Visit 1) and during the Run-In Period.

All prior and concomitant medications (prescription and over-the-counter), vitamin and mineral supplements, and herbs taken by the subject in the past 30 days will be recorded in the Prior & Concomitant Medication electronic case report form (eCRF) and will include start and stop date, dose and route of administration, frequency, and indication. Medications taken for a procedure should also be included.

## **7 COLLECTION OF STUDY VARIABLES**

### **7.1 Recording of Data**

The Investigator will ensure that data collected during this study are recorded in the electronic data capture (EDC) system in the corresponding eCRFs. The Investigator will ensure accuracy, completeness, and timeliness of the data recorded and of the provision of answers to data queries. Any completed eCRF must be signed by the Investigator. A copy of the completed eCRF will be archived.

### **7.2 Data Collection Prior to Enrollment**

At Screening (Visit 1), the following information will be collected from every participant to identify eligible subjects for further assessments:

- Assessment of the disease status outlined in the inclusion/exclusion criteria
- Date of birth, gender, and race
- Weight (pre-dialysis) and height (kg and cm, respectively)
- Kt/V – most recent value prior to Screening
- Medical and surgical history
- Phosphate binder currently used and prescribed daily dose (must be three times a day)
- Physical examination
- Vital signs (pre-dialysis)
- Electrocardiogram evaluation
- Blood sample for clinical laboratory chemistry and hematology tests (pre-dialysis)
- FSH and pregnancy test, if applicable
- Concomitant medications

### **7.3 Safety Variables**

Safety assessments will be performed during the study and will include physical examinations, body weight, vital signs, safety laboratory tests, 12-lead ECG, and AE recording. Body weight, vital signs, and blood collections for laboratory assessments **must** be

performed pre-dialysis. All other assessments may be performed pre-, during, or post-dialysis but should be performed at the same time at each visit.

### **7.3.1 Physical Examination**

The physical examination will include an assessment of the following items: general appearance, skin (including any pitting edema in lower legs or feet), cardiovascular, respiratory, abdomen, lymph nodes, musculoskeletal, and neurological systems. Any findings or absence of findings relative to each subject's physical examination will be carefully documented in the eCRF.

### **7.3.2 Vital Signs (blood pressure and heart rate)**

Blood pressure and heart rate will be obtained at all visits (pre-dialysis). Systolic and diastolic blood pressure will be measured after the subject has been in sitting or supine position for at least 5 minutes. All measurements will be recorded on the source document and in the eCRF.

### **7.3.3 Electrocardiogram**

A 12-lead ECG will be performed after the subject has been in a sitting or supine position for at least 5 minutes.

The following ECG parameters will be recorded: heart rate, PR-interval, QRS-duration, QT-interval (uncorrected), QTc-interval (corrected), RR-interval and the Investigator's conclusion on the ECG profile.

The Investigator will assess whether the ECG is normal or abnormal; abnormal will be further subdivided into clinically significant and not clinically significant.

Electrocardiographic intervals and the Investigator's assessment of all abnormal ECGs will be recorded in the eCRF.

Additional ECGs may be obtained if clinically indicated.

### **7.3.4 Clinical Laboratory Tests**

Samples **must** be obtained, pre-dialysis, for the hematology and chemistry clinical laboratory tests identified in [Table 7-1](#).

Other evaluations and tests performed at Screening (Visit 1) and other visits, as specified in the Schedule of Assessments and Procedures ([Section 1.3](#)), will include:

- FSH test, if applicable
- Pregnancy test, if applicable

**7.3.5 Analysis of Clinical Laboratory Tests**

A certified laboratory will be used to process and provide results for the clinical laboratory tests. The baseline laboratory test results for clinical assessment for a particular test will be defined as the last measurement prior to the initial dose of study medication.

For any laboratory test value outside the reference range that the Investigator considers clinically significant, the Investigator will:

- Repeat the test to verify the out-of-range value.
- Follow the out-of-range value to a satisfactory clinical resolution.

Record as an AE any laboratory test value that (1) is confirmed and the Investigator considers clinically significant, or (2) that requires a subject to be discontinued from the study, or (3) that requires a subject to receive non-study treatment, or (4) fulfills one or more criteria for serious adverse event (SAE).

**Table 7-1: Clinical Laboratory Tests**

Hematologya	Chemistryb	Otherd
Hematocrit Hemoglobin Red blood cell (RBC) count White blood cell (WBC) count Neutrophils (%) Lymphocytes (%) Monocytes (%) Basophils (%) Eosinophils (%) Platelet count	Albumin Alanine aminotransaminase (ALT) Aspartate aminotransaminase (AST) Alkaline phosphatase Bilirubin, total Bicarbonate Blood urea nitrogen (BUN) Calcium, total Chloride Creatinine Creatine kinase Glucose Magnesium Phosphorus c Potassium Sodium	FSH Serum pregnancy

a Whole blood.

b Serum.

c Serum phosphorus is also performed separately from standard clinical laboratory tests at protocol-specified time points.

d FSH and serum pregnancy tests are performed on all females <60 years of age unless there is a documented method of sterilization, or FSH test confirms post-menopausal status.

## **7.4 Adverse Events**

The Investigator is responsible for ensuring that all staff involved in the study are familiar with the content of this section.

An AE is defined as any untoward medical occurrence in a subject administered a pharmaceutical product during the course of a clinical investigation. An AE can therefore be any unfavorable and unintended sign, symptom, or disease temporally associated with the use of an investigational product, whether or not thought to be related to the investigational product.

Subjects will be monitored throughout the study for AEs, from Screening (Visit 1) through the end of the study. Medical events that occur before Screening (Visit 1) and are ongoing at Screening (Visit 1) should be recorded as medical history, not AEs. All AEs spontaneously reported by the subject or reported in response to the open question from the study personnel such as “Have you had any health problems since the previous visit?”, or revealed by observation will be collected and recorded in the AE eCRF. When collecting AEs, the recording of diagnoses is preferred (when possible) to recording a list of signs and symptoms. In instances of well-recognized symptoms, they can be recorded as the commonly used diagnosis (e.g., fever, runny nose, and cough can be recorded as “flu”). However, if a diagnosis is known, but there are other signs or symptoms that are not generally part of the diagnosis, the diagnosis and each sign or symptom should be recorded separately.

Adverse events that are identified as specified in the protocol must be recorded on the AE eCRF with the status of the AE noted. Each AE must be followed until it is resolved or stabilized, or until all attempts to determine resolution of the AE are exhausted. All AEs that are ongoing at the end of study will be recorded as ongoing in the eCRF. The procedures specified in [Section 7.4.8](#) are to be followed for reporting SAEs.

### **7.4.1 Adverse Events Associated with Change in Stool Form and/or Frequency**

Based on tenapanor’s ability to inhibit the absorption of dietary sodium, it is known to alter stool form and frequency in some subjects. For a change in stool form and/or frequency to be considered an AE, the subject must consider the bowel movements to be “bothersome”.

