### **7.4.2 Recording Adverse Events**

Adverse events are to be recorded on the AE eCRF. Severity of an AE will be graded according to the following definitions:

- Mild: The subject experiences awareness of symptoms but these are easily tolerated or managed without specific treatment.
- Moderate: The subject experiences discomfort enough to cause interference with usual activity, and/or the condition requires specific treatment.
- Severe: The subject is incapacitated with inability to work or do usual activity, and/or the event requires significant treatment measures.

Action taken will be categorized as dose not changed, dose reduced, drug interrupted, drug withdrawn, required concomitant medication, required concomitant procedure, and/or other.

Event outcome at resolution or time of last follow-up will be recorded as not recovered/not resolved, recovered/resolved, recovered/resolved with sequelae, recovering/resolving, fatal, or unknown.

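### Section 7.4.1 can keep a stool change that altered treatment, or had a serious outcome, out of the adverse event tables if the subject does not call it bothersome

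*Combined protocol and SAP*

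**What the plan says.** Section 7.4.1 notes that tenapanor is known to alter stool form and frequency, and then sets a special rule: "For a change in stool form and/or frequency to be considered an AE, the subject must consider the bowel movements to be" bothersome. No other route to adverse event status is given for a stool change.

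The related rules are these:

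- **General definition (7.4).** "An AE is defined as any untoward medical occurrence in a subject administered a pharmaceutical product during the course of a clinical investigation". The subject's opinion is not part of it.
- **Dose changes (6.1.3).** Between randomization and Day 15, "doses can be adjusted in 10 mg increments based on s-P levels and/or GI tolerability". No adverse event is required first.
- **Action taken (7.4.2).** "Action taken will be categorized as dose not changed, dose reduced, drug interrupted, drug withdrawn, required concomitant medication, required concomitant procedure, and/or other". This stands in the section on recording adverse events.
- **Laboratory values (7.3.5).** An abnormal value becomes an adverse event if it is confirmed and clinically significant, or forces discontinuation from the study; the last two triggers read "3) that requires a subject to receive non-study treatment, or (4) fulfills one or more criteria for serious adverse event (SAE".
- **Serious events (7.4.7).** The definition takes an adverse event as its starting point and adds outcome criteria.
- **Safety output (9.4.9).** Treatment-emergent adverse events are tabulated by system organ class and preferred term. No stool summary or dose-change summary is named.

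**The concern.** Looser and more frequent stools are the effect that the protocol itself expects from the drug's mechanism (2.4), and gastrointestinal tolerability is one of its two stated reasons for changing the dose. Suppose an investigator lowers the dose because of frequent loose stools in a subject who says they are no bother. On the wording of 7.4.1 there is no adverse event, so there is no dose-reduced entry against one and nothing in the tables. Because 6.1.3 also permits changes for serum phosphorus, that reduction may be hard to tell apart afterwards from one made for efficacy.

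At stake is whether the reported tolerability profile agrees with what was done to the subjects' treatment. The primary efficacy analysis is not affected, and no safety hypothesis is tested (9.4.1).

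**Working it through.** The plan states no figure on this point, so the check is a reading of the rules in sequence, followed by an illustration on assumed rates.

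**Does anything override 7.4.1?**

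1. *General definition, 7.4.* It is broad, and 7.4 also collects events revealed by observation. But 7.4.1 is the specific rule for stool changes, and a site would follow the specific rule.
2. *Severity, 7.4.2.* The Moderate grade includes "The subject experiences discomfort enough to cause interference with usual activity, and/or the condition requires specific treatment". A treated stool change would therefore rank at least Moderate, but grading begins only once the event is an adverse event. This is no override.
3. *Serious events, 7.4.7.* The definition presupposes an adverse event, so its wording does not bring back an event that 7.4.1 excludes.
4. *Laboratory rule, 7.3.5.* It works by consequence, as a stool rule could, but it covers laboratory values only.
5. *Dose adjustment, 6.1.3.* It requires neither an adverse event nor, in the protocol text, a recorded reason.

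None of these sections supplies an exception.

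**What else would show the event?**

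- The concomitant medication form records a treating drug with its indication (6.5).
- Dispensing records hold dates and amounts (6.2.2).
- The schedule in 1.3 has no stool diary or stool assessment. It places safety laboratory tests only at Visits 1 and 8, so during the titration window adverse event enquiry is the main source on stool tolerability.
- None of these other records feeds the adverse event tables in 9.4.9.

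**Direction.** The condition can only remove stool events from an arm's count. If *p* is the true rate of treatment-altering stool changes and *u* the share not called bothersome, the recorded rate is *p*(1 − *u*), which is never above *p*. If *u* is the same in both arms, the difference between arms shrinks by the factor (1 − *u*). If *u* differs by arm, only the direction within each arm is certain.

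**Size, by assumption only.** The documents give neither *p* nor *u*. With 107 tenapanor subjects (9.2), *p* assumed at 10% to 30% and *u* at 10% to 25%:

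- low: 107 × 0.10 × 0.10 = 1.1 subjects (1.0% of the arm)
- high: 107 × 0.30 × 0.25 = 8.0 subjects (7.5% of the arm)

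The range shows scale and is not an estimate. No corresponding figure can be given for placebo.

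**The case against.** The best defence is that this is a deliberate and openly stated convention. Section 2.4 describes looser stools as intended and wanted in some subjects, while 7.4 speaks of what is unfavorable and unintended: "An AE can therefore be any unfavorable and unintended sign, symptom, or disease temporally associated with the use of an investigational product". On that view 7.4.1 simply says when a known drug effect becomes untoward. For simple softening this stands, and the convention should stay. It does not reach a stool change bad enough to be treated or to alter dosing.

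The failure case is also narrow. With no stool diary, the investigator will usually hear of stool changes from the subject, and a subject whose stools justify action will mostly call them bothersome. That stands too, and it limits the size but not the direction. Consequences such as dehydration or an electrolyte disturbance are not stool changes and can be adverse events in their own right.

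A reader might infer two stronger points that the documents do not support:

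- **That 7.4.1 contradicts 7.4, 7.4.2 and 7.3.5.** The general definition can be read consistently with it for intended softening. A stool change can be bothersome and still Mild, since that grade reads "The subject experiences awareness of symptoms but these are easily tolerated or managed without specific treatment". The laboratory rule governs a different kind of data, so it is an analogy and not a conflict.
- **That these events leave no trace.** Treating drugs and dispensing are recorded. The case report forms are not in the documents, so a dosing form that captures reasons for change cannot be ruled out. What the text supports is that the events may be absent from the adverse event tables.

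**Conclusion.** The point holds in a narrow form. As written, a stool change that led to reduction, interruption or withdrawal of study drug, led to treatment, or had a serious outcome need not be recorded as an adverse event if the subject does not find it bothersome. It could then be missing from the planned tables and have no action-taken entry.

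The bias in the recorded counts is toward understating gastrointestinal toxicity. Its size is not derivable from the documents and may be small; 1 to 8 subjects of 107 rests entirely on assumed rates. That more such events would fall in the tenapanor arm is an inference from the pharmacology in 2.4, not a documented rate. The conclusion also assumes that sites apply 7.4.1 literally. This is an inexpensive improvement to safety reporting and does not challenge the trial's primary result.

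**What to change.** Keep the bothersome convention for simple softening and add one sentence to 7.4.1, repeated in the case report form instructions:

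*A stool change is also recorded as an adverse event, whether or not the subject finds it bothersome, if it leads to reduction, interruption or withdrawal of study medication, leads to non-study treatment, or meets an outcome criterion for a serious adverse event.*

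This extends the consequence-based approach that 7.3.5 already takes for laboratory values. It is not a copy of that rule: 7.3.5 lists discontinuation from the study, non-study treatment and serious criteria, so the triggers for dose reduction and interruption are new and should be adopted knowingly. The sentence governs recording only and does not change when or how doses are adjusted.

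The cost is one sentence and a line of site guidance, with no new visit, test or form. The downside is that the reported gastrointestinal adverse event rate may be slightly higher.
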